Title: STAND ALACRITY CENTER Signature Project: STAND Triaging and Adapting to Level of Care

Lay title: STAND Finding and adapting the level of care

Research study IRB# 22-000635

[figure not shown]
Protocol version: 01/26/2026

Research Description

The STAND ALACRITY CENTER Signature Project: STAND Triaging and Adapting to Level of Care study is a randomized controlled trial comparing 2 approaches for treatment triaging and adaptation. This study is being conducted among community college students enrolled in the Screening and Treatment for Anxiety and Depression (STAND) initiative at East Los Angeles College (ELAC). 1,000 students who meet study eligibility criteria will be enrolled over 5 years. Participants will be randomized to receive care under 1 of 2 models: symptom severity-based decision making (SSD) or data-driven decision making (DDD). Participation involves completing online self-report assessments in addition to engaging in an assigned depression or anxiety service as provided by this study. See **Figure 1** for general overview of the research design.

This study is funded by the National Institute of Health – National Institute of Mental Health. This research study is conducted by [name], from the Departments of Psychology and Psychiatry, and [name], from the Department of Psychiatry, at UCLA. This study is affiliated with the UCLA Depression Grand Challenge.

Figure 1

Sample

This study aims to enroll approximately 200 participants per year, for a total sample size of 1,000 participants over five years. To reach this sample size, we expect to consent up to 5,000 students.

Eligibility

Interested individuals are directed to the study webpage to learn about STAND at ELAC, and create an online account. Initial study eligibility is assessed through self-report questions administered during the account creation process. All individuals are informed during screening that they are welcome to sign up for the free virtual wellness program Stand For All, without participating in this research study. If an individual is deemed ineligible at any point during screening, they are notified and offered alternative resources, including Stand For All.

Inclusion criteria:

- Age 18 – 40 years
- Competent to understand informed consent and express willingness to follow study procedures.
- Currently enrolled ELAC student
- Either uninsured or on California Medicaid (Medi-Cal).
- Proficient in English
- Have private access to internet

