Exclusion criteria:

- Unable to comprehend the consent form fully, respond adequately to screening questions, or maintain focus or to sit still during assessment.
- Primary psychotic disorder, and disorders requiring more specialized care such as: severe eating disorders, substance use disorders, uncontrolled medical conditions, marked cognitive impairment, or severe neurological disorder.
 - Note: Substance use is expected in this adult population. Exclusion will be only for substance abuse or dependence that is so severe that it interferes or would foreseeably interfere with the ability to complete assessments or intervention.
- Previous participation in STAND research studies

Preliminary eligibility is established during the account creation process. If responses to the self-report questions in screening indicate the individuals may have a substance use disorder, psychosis, or active suicidality, they will be contacted by staff to further assess eligibility for this program, and resources/referrals for care may be provided if they are determined ineligible for this study. If they are found eligible after assessment, they will be provided a link to re-enter the screening process to complete surveys, then receive a randomized condition assignment and information about proceeding to their recommended level of care. Further confirmation of insurance coverage may be required in the case that a participant is assigned to receive clinical care. If they do not have eligible insurance coverage, they are informed of ineligibility at that time. Participants who are treated by a mental health professional (such as a psychiatrist, psychologist, therapist, etc.) during time that treatment is offered through STAND and unwilling to fully transfer care to STAND, will not be eligible to receive clinical services, but may continue participating in the study through receiving surveys. If there are changes to their current treatment status they may be offered to transition care to STAND, or they may be transitioned to other levels of care (tiers 1 or 2) as recommended by their condition assignment (SSD or DDD). Eligibility may be reassessed throughout the study by research staff, coaches or care providers. If at any time a participant is found to not meet eligibility criteria, they will be informed of ineligibility and removed from study.

Study Overview

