Study participation is completely remote and lasts 40 weeks after initial orientation/intake. Participation requires creating an online account on the STAND at ELAC study website in order

to complete eligibility screening. Once initial eligibility is confirmed, those who choose to participate must sign an online consent form and complete baseline assessments. Upon completion of baseline assessments, participants are randomized to 1 of 2 treatment conditions (SSD or DDD), and assigned to a level of care based on their responses to baseline surveys. Participants must attend a remote orientation or intake session for their assigned level of care, and thereafter are asked to complete weekly online surveys over the course of 40 weeks. Participants are considered enrolled after completing consent, baseline assessments, and attending an orientation/intake session for their assigned level of care.

Condition Assignment

Participants in this study will be randomized into one of two conditions which are differentiated by approach for decision making in treatment triage and treatment adaptation. The standard approach used in previous STAND studies is **symptom severity-based decision making (SSD)**. SSD participants will be triaged and adapted to level of care based on reported symptom severity only.

The experimental approach is **data-driven decision making (DDD)**. DDD participants will be triaged and adapted to a level of care using a multivariate predictive algorithm that is iteratively updated annually. This algorithm determines level of care based on individual participant characteristics, coupled with reported symptom severity. The DDD *triaging* algorithm will be implemented beginning in Year 1 of this project and the DDD *adaptation* algorithm will be implemented beginning in Year 2.

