- III. **Clinical care** – participants with severe depressive symptoms or significant suicidality on the CAT-MH will be allocated to access clinical care, which provides weekly psychotherapy sessions and - if indicated - psychiatric care may additionally be provided. While clinical care will be available for the entire length of the study, participants will be informed that on average therapy is completed within 13 sessions. The schedule of psychiatric care will be determined by the provider. Information from treatment appointments will be collected for use as study data. Treatment appointments take place via phone, secure videochat or in person, in accordance with local public health guidelines and clinical considerations. Clinical care will be provided by DMH Clinicians at the UCLA Tele-Mental Health Clinic, who will follow standard of care clinical protocols developed by STAND and the clinical operational protocols established within their institutions (modified for this implementation).

Service eligibility is confirmed throughout the participation by research staff, coaches and clinicians associated with participants' care. If a participant becomes ineligible to continue clinical care through STAND (e.g., endorses psychosis or severe substance use disorder), they will be referred out to alternative care providers, but may continue to receive surveys and for the duration of the study. These individuals may also be offered re-entry to appropriate levels of care once their completion of outside care is confirmed.

Participants might receive treatment adaptation during their participation in the study. Treatment adaptation involves moving to a different level of care if indicated by the criteria of the participant's assigned condition, SSD or DDD. In any case that a participant endorses suicidality they are offered adaptation to receive clinical care.

Study participation lasts 40 weeks, and the average length of intervention is less than 13 weeks. Once participants complete their assigned level of care (Wellness, Coaching, or Clinical care) they will continue to receive weekly surveys until the end of their 40 week participation period. Responses will continue to be monitored in this period, and additional care and resources will be offered if survey responses indicate need.

Technology-enhanced suicide prevention intervention (TE-SPI):

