outcome) from baseline data, current tier and weeks 1-12 outcomes, we will use the model-based estimates for the fixed-effects (baseline and current tier), and the empirical Bayes estimates (see Hedeker and Gibbons, 2006189) for the random effects that describe the trajectory of the outcome based on the repeated assessments through 12 weeks. These fixed and random coefficient estimates will then be used to predict the distal endpoint (16 weeks) and based on this estimated outcome, treatment adaptation will be performed. Model selection will be based on minimizing the root mean square error (RMSE) between the actual observed 8-week outcomes and the estimated outcomes. Once calibrated, we will use this predictive model to set thresholds on what level of change or lack thereof will lead to adaptation of level of care (tier shift) at 4-week intervals of treatment rather than having to wait for several months to evaluate outcomes. The algorithm will be designed such that it will predict the lowest level of care that would produce improvement in symptoms at the outcome point.

Specific Aim 3:

Adapting Level of Care - Evaluate whether data-driven algorithms for adapting level of care lead to greater treatment adherence and outcomes than symptom severity adaptation (Years 2-5). Hypothesis a: Compared to SSD, DDD will show greater treatment adherence (session/lesson completion), greater improvements in depression and anxiety symptoms and social, family and academic functioning at 16 weeks, 24 weeks, 32 weeks, and 40 weeks. Hypothesis b: between-group differences will increase annually with refinements to DDD algorithms.

Analysis:

- Adaptation Outcomes: Outcome analyses will be conducted in three different ways similarly to the analyses planned for the triaging treatment outcomes. Secondary analyses will also be performed. These include 1) using a linear mixed model to explore mediating factors and 2) performing cost-effectiveness analyses of the adaptation algorithm.

Specific Aim 4:

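### Participants found ineligible after randomisation are to be removed from the study, which conflicts with the intent-to-treat primary analysis and with the protocol's own survey-only provision

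*Protocol*

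**What the plan says.** **Removal.** The text after the exclusion criteria in the protocol's Eligibility section says "Eligibility may be reassessed throughout the study by research staff, coaches or care providers", and then "If at any time a participant is found to not meet eligibility criteria, they will be informed of ineligibility and removed from study".

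**Insurance.** The same paragraph says "Further confirmation of insurance coverage may be required in the case that a participant is assigned to receive clinical care", and continues "If they do not have eligible insurance coverage, they are informed of ineligibility at that time". It does not say whether this means ineligible for the study or only for clinical care.

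**Order of events.** Under Study Overview, SSD/DDD randomisation follows the baseline assessments and the tier is assigned after that. Under Condition Assignment, the tier follows the rule of the randomised condition. A person counts as enrolled only after attending intake or orientation for the assigned tier.

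**Survey-only participation.** Eligibility lets people treated elsewhere, who do not transfer their care, remain in the study through surveys. Levels of Care says of participants who become ineligible for clinical care, with psychosis and severe substance use disorder as examples, that "they will be referred out to alternative care providers, but may continue to receive surveys" for the duration of the study.

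**Analysis.** Specific Aim 1 makes the intent-to-treat analysis primary, and Specific Aim 3 follows the same scheme.

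**The concern.** An intent-to-treat comparison needs outcomes sought from everyone randomised, whatever happens to their services afterwards. The removal sentence lets study staff end follow-up after randomisation. Two of the routes to removal lie downstream of the randomised arm or of the participant's course:

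- The insurance confirmation is described for people assigned to clinical care, and the arm's rule decides who they are.
- Psychosis and severe substance use can emerge during follow-up. The weekly CAT-MH covers both, so the rule can be triggered at any time.

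If losses differ by arm, or fall on those doing worst, the participants observed at weeks 8 to 40 are no longer comparable by randomisation. This cannot be left to the SAP, because no analysis recovers surveys that were never sent.

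**Working it through.** The protocol states no figure for this loss, so the first three steps set the sections side by side. The fourth sizes the effect under assumptions.

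**1. Is the check downstream of arm?** The sequence is baseline, randomisation, tier by the arm's rule, then possible insurance confirmation for Tier III. In SSD, Tier III follows severe depression or suicidality. DDD adds other variables. Opportunities to change tier also differ: SSD once after week 16, DDD every 4 weeks in Year 2 and every 8 weeks in Years 3-5. The same student can therefore meet the check in one arm and not in the other, or at a different time.

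**2. Do the sections agree?** Psychotic disorder and severe substance use are exclusion criteria. Under Eligibility, a participant found to have either is removed from the study. Under Levels of Care, a participant who loses clinical care for either reason may stay on surveys. Staff could follow either text for the same person.

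**3. Who is counted?** A person who fails the insurance check after randomisation but before intake has been randomised without being enrolled. If the 1,000 are counted as enrolled, this person appears nowhere.

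**4. How large could it be?**

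Inputs from the protocol:
- Planned Tier III share, both arms together (Recruitment): 60/(20 + 120 + 60) = 30%. No split by arm is given.
- Detectable final difference (power statement before Specific Aim 5): 0.26 SD, used here only as a yardstick. With a linear-trend contrast over four visits starting from no difference, a two-sided 5% test gives 0.256 and the stated one-sided test 0.227. Nothing below depends on which was used.

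Assumptions, none in the protocol: a fraction x of 5-20% of Tier III fails the check; failing ends follow-up; Tier III is g = 1.0-1.5 SD worse than the rest; Tier III shares p are 40% and 20% in the two arms (average 30%).

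Fraction of an arm lost = p·x. Shift in the arm's observed mean = g·p − g·p(1 − x)/(1 − p·x). Bias = difference between the two shifts.

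| x | g | Lost, p = 40% v 20% | Shift, p = 40% | Shift, p = 20% | Bias (SD) |
|---|---|---|---|---|---|
| 5% | 1.0 | 2% v 1% | 0.400 − 0.380/0.980 = 0.012 | 0.200 − 0.190/0.990 = 0.008 | 0.004 |
| 20% | 1.5 | 8% v 4% | 0.600 − 0.480/0.920 = 0.078 | 0.300 − 0.240/0.960 = 0.050 | 0.028 |

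At shares of 35% v 25% the range is 0.002-0.014. At 30% in both arms it is zero.

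As a bounding illustration of outcome-dependent removal, suppose the worst fraction q is removed from one arm only. The mean shifts by φ(z)/(1 − q), with φ the standard normal density and z the 1 − q quantile. For q = 1%, 2%, 3% and 5% this is 0.027, 0.049, 0.070 and 0.109 SD, or 10% to 42% of 0.26. Real removals would not all come from one arm's extreme, so this is a ceiling for a given q and not a forecast.

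**The case against.** **Insurance.** A reader might infer that insurance is re-checked only in Tier III. The protocol does not say so. Insurance is an entry criterion for all and is asked of everyone at baseline (Table 2), the further confirmation only may be required, and general reassessment is open to staff in every tier. It is also unclear that failing the check ends the study. This stands. What remains is that the one insurance confirmation described after randomisation is tied to an arm-determined tier.

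**Student status.** A reader might infer that anyone who leaves college is removed, because "Currently enrolled ELAC student" is an entry criterion, and that the Aim 3 comparison of "social, family and academic functioning at 16 weeks, 24 weeks, 32 weeks, and 40 weeks" then loses those with the worst academic results. No re-check of enrolment is scheduled. Students also leave by transferring or graduating, so the direction of any such loss is unknown. The documents do not support that claim.

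**Existing safeguards.** Survey-only participation exists for some, and Levels of Care can be read as the specific rule and Eligibility as the general one. Suicidality leads to an offer of clinical care in both arms, so part of Tier III entry does not depend on arm. These points narrow the problem. They do not remove the unqualified sentence or say which text governs.

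**Removal is not exclusion from analysis.** No section says that data already collected are dropped, and the handling of missing data may be in the SAP. It is therefore too strong to say that the arms analysed will not be the randomised arms. But stopping the surveys creates the missing data, and that is fixed in the protocol.

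**Size.** The insurance route looks small, and the protocol does not say whether its 5% drop-out per period already includes removals.

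**Conclusion.** The point holds as a conflict in the protocol and a structural risk. It is not a demonstrated bias. Taken literally, the removal sentence stops outcome collection after randomisation in ways that can depend on arm and clinical course. It sits badly with the intent-to-treat primary analysis and contradicts Levels of Care for overlapping conditions. The definition of enrolment can hide losses before intake.

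The size is unknown. The insurance route alone is 0 to about 0.03 SD under the assumed failure rates, severity gaps and tier shares, and zero if both arms send equal shares to Tier III. Outcome-dependent removal could matter more, but the protocol gives no rate for it. The case for change rests on the fact that outcomes not collected cannot be restored, and on the low cost of collecting them.

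**What to change.** - **Eligibility:** state that ineligibility found after SSD/DDD randomisation affects access to services only. The participant is still offered the survey schedule to week 40, unless consent is withdrawn or the person can no longer competently take part, and is analysed in the randomised arm.
- **Analysis set:** define intent-to-treat as all randomised, not all enrolled.
- **Consistency:** reconcile Eligibility with Levels of Care, and say whether a failed insurance confirmation concerns the study or clinical care alone.
- **Reporting:** tabulate ineligibility found after randomisation by arm and tier, including cases before intake.
- **Insurance:** confirm it before randomisation where feasible. Otherwise keep those who fail later on surveys and in the intent-to-treat set. Checking everyone is optional, since about 70% of planned places (140 of 200) are outside Tier III.

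The cost is protocol wording and extra survey payments of at most 5 × $20 + 35 × $10 = $450 per participant kept. Survey-only participation already exists in the protocol, and no rule on who receives which service needs to change for this purpose.

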For receiving care, participants will be assigned to one of the three services: Wellness (Tier I), Digital Mental Health and Coaching (Tier II) or Clinical Care (Tier III) based on the criteria of their randomized condition - SSD or DDD. Participants in both conditions will be asked to complete short surveys online weekly, and longer online survey assessments every 8 weeks. At every assessment time point participants are asked to complete the CAT-MH (computer adaptive tests) which provides validated symptom scores for depression, anxiety, mania/hypomania, substance use, psychosis, and suicidality. See **Table 1** for a description of CAT-MH depression and anxiety scores and their clinical interpretation. The information about depression and anxiety symptoms collected during these CAT-MH assessments will be used to inform adaptation of care in accordance with the criteria of participant's randomized condition, SSD or DDD.

Participants assigned to tiers 2 & 3 (in both SSD and DDD conditions) will additionally be randomized to receive usual risk management (URM) or usual risk management with the addition of a technology-enhanced suicide prevention intervention (TE-SPI).

Table 1 CAT-MH Symptom Scores

	Depression (CAT-DI)	Anxiety (CAT-ANX)
Normal	0 - < 35	0 - < 35
Mild	35 - 65	35 - 50
Moderate	> 65 - 75	> 50 - 65
Severe	> 75 - 100	> 65 - 100

In **SSD, triaging** will be determined solely by scores on CAT-DI (depression symptom severity), CAT-ANX (anxiety symptom severity) and CAT-SS (suicide risk severity). CAT-DI and CAT-ANX

provide cutoffs for none, mild, moderate and severe categories. From CAT-SS (suicidality), participants who endorse suicidal ideation with either intention or plan are considered at risk, and are offered Tier III clinical care. Otherwise, Tier assignments in SSD are made based on the following criteria:

- Tier I self-guided prevention (Wellness): Participants with less than mild depression or anxiety and without suicidality.
- Tier II (Digital Mental Health with Coaching): Participants with mild to moderate depression or mild to severe anxiety, without suicidality.
- Tier III (Clinical care): Participants with severe depression or endorsement of suicidality.

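### Enrolled status, weekly surveys and the 40-week clock start at an orientation held after SSD/DDD randomisation, while other sections start them earlier, so follow-up of randomised non-attenders is unclear

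*Protocol*

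**What the plan says.** The Study Overview sets the order of events. Randomisation comes first: "Upon completion of baseline assessments, participants are randomized to 1 of 2 treatment conditions (SSD or DDD"). Orientation follows: "Participants must attend a remote orientation or intake session for their assigned level of care, and thereafter are asked to complete weekly online surveys". Enrolment is then defined: "Participants are considered enrolled after completing consent, baseline assessments, and attending an orientation/intake session for their assigned level of care". The clock starts at the same session: "Study participation is completely remote and lasts 40 weeks after initial orientation/intake".

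Condition Assignment says that the tier is assigned "based on the criteria of their randomized condition - SSD or DDD". The orientation or intake a student must attend is therefore a consequence of the randomised arm.

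The Research Description gives the target: "1,000 students who meet study eligibility criteria will be enrolled over 5 years". The Sample section adds: "To reach this sample size, we expect to consent up to 5,000 students". The power statement, printed at the end of the Specific Aim 4 analysis, uses 1,000 students, 500 per arm, with 5% drop-out from one assessment period to the next. The Specific Aim 1 analysis makes intention to treat primary and has outcomes assessed weekly up to week 8.

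Other sections run differently:
- Specific Aim 5 and Project 1 Engagement Interventions put an uptake randomisation at enrolment, ahead of the SSD/DDD randomisation.
- Assessments sends students to the baseline link once enrolment is complete, and has the CAT-MH repeated weekly from baseline.
- The Table 2 footnote counts all later time points from completion of the baseline CAT-MH.
- Assessments also allows baseline surveys to be repeated when care starts more than 4 weeks after baseline.
- Condition Assignment states, with no attendance condition: "Participants in both conditions will be asked to complete short surveys online weekly, and longer online survey assessments every 8 weeks".

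**The concern.** Attendance at orientation happens after randomisation and can be affected by it. The same student may be sent to different tiers under SSD and DDD, and the tiers ask for different things. If the arms differ in who attends, a comparison limited to attenders no longer has the protection of randomisation.

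Intention to treat needs outcomes from everyone randomised. A statistical analysis plan can define that population later, but it cannot supply surveys that were never sent. Who is surveyed, and from which date, is therefore a matter for the protocol, and here its sections disagree.

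A second difficulty is the time origin. If week 8 can be counted from baseline or from orientation, it falls at different points of care. A baseline repeated after randomisation would also create a second possible starting value, taken when the student already has a tier.

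**Working it through.** No figure in the protocol is disputed. The check sets the sections side by side and uses arithmetic only to show what depends on which reading.

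**1. Position of enrolment relative to SSD/DDD randomisation**
- Study Overview: consent, baseline, randomisation and tier, orientation, enrolled. Enrolment is after randomisation.
- Assessments: enrolled, then baseline. Enrolment is before randomisation.
- Specific Aim 5 and Project 1 Engagement Interventions: enrolled, uptake randomisation, SSD/DDD randomisation. Enrolment is before SSD/DDD randomisation.

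These cannot all hold.

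**2. What the 1,000 counts**

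Under the Study Overview meaning, number randomised = 1,000 + randomised non-attenders. At most 5,000 − 1,000 = 4,000 students leave between consent and enrolment. Baseline and randomisation both lie inside that interval, so the number randomised is somewhere from 1,000 to 5,000. The protocol does not split the loss into before and after randomisation, so this is a bound and not an estimate. The 5% drop-out in the power statement applies between assessment periods and is not said to cover loss at orientation.

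**3. Which outcomes depend on attendance if the Study Overview governs**
- Its wording makes the weekly surveys follow orientation. For Aim 1, weeks 1 to 8 comprise 7 weekly surveys (weeks 1 to 7) and one 8-weekly assessment (week 8). Seven of the 8 time points are affected.
- Over the whole study, Financial obligation and compensation lists 35 weekly and 5 eight-weekly assessments, so 35 of 35 + 5 = 40 are affected.
- The stated between-arm comparisons are at week 8 (Aim 1) and at weeks 16, 24, 32 and 40 (Aim 3). All are 8-weekly time points. They are affected only if the 8-weekly assessments also wait for orientation, which the text leaves open.
- Adherence is a count of sessions or lessons completed and does not depend on survey response.

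**4. The two clocks**

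Let orientation fall k weeks after baseline. The protocol does not give k, so 1 to 4 weeks is assumed here.
- Week 8 from baseline is 8 − k weeks after orientation: 7 weeks for k = 1, 4 weeks for k = 4.
- Forty weeks from orientation ends at week 40 + k from baseline: week 41 to week 44.
- If weekly surveys start at orientation but are numbered from baseline, even attenders are not asked for k of the 7 surveys before week 8, that is 1 to 4 of them.

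Assessments foresees gaps above 4 weeks between baseline and start of care. A repeat baseline then comes after randomisation, because the tier is already assigned. The text does not say whether the repeat resets the Table 2 clock.

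**The case against.** The strongest reply is that the endpoints tested between arms are not shown to be at risk. Condition Assignment addresses both conditions without mentioning attendance. Assessments sends the scheduled online surveys by email or text at weeks counted from baseline. Read that way, everyone randomised receives the 8-weekly assessments, and the Study Overview needs only a clarifying sentence. This stands as a possible reading and limits the point. It does not remove the Study Overview's own wording, or the Aim 1 statement that outcomes are collected weekly to week 8.

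A second reply is that the Study Overview holds the only explicit definition of enrolment. The description of the STAND-as-usual uptake condition supports it by treating orientation as part of the enrolment process, so the other uses may simply be loose. If so, the definition that selects after randomisation is the governing one, which strengthens the concern. A reader might also see a conflict in the Consent section. The signature it describes is only one of the steps that the Study Overview itself requires, so it is not counted here.

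A third reply is that Table 2 places orientation between baseline and week 1, and that repeating baseline after a long delay may keep the clocks close. That may limit the gap in practice, but neither provision fixes the origin.

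Two stronger readings are tempting. A reader might infer that non-attenders are not followed at all and that the intention-to-treat analysis must lack their endpoints; the provisions for 8-weekly assessments do not support that. A reader might also take the difference between 5,000 and 1,000 as loss after randomisation; many of those students may stop before baseline, and the protocol gives no split.

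**Conclusion.** The contradiction is real and should be fixed. As written, the Study Overview leaves randomised non-attenders out of the weekly outcomes and out of the 1,000, while the primary analysis is by intention to treat. Other sections support a different order and a different clock. It is not established that non-attenders go unsurveyed at week 8 or later.

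The size of any bias or loss of power cannot be derived, because neither the number of randomised non-attenders nor its balance between arms is given. The 7-of-8 and 35-of-40 counts hold only if the Study Overview governs and only for weekly surveys. The clock figures rest on the assumed delay of 1 to 4 weeks. If practice already follows the baseline-timed sections, the problem is one of wording.

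**What to change.** 1. State in the Study Overview that outcome assessments, at least week 8 and the later 8-weekly ones, go to everyone randomised whether or not they attend orientation, and that the intention-to-treat analysis includes them.
2. Use one time origin, the baseline CAT-MH as in the Table 2 footnote. Keep the pre-randomisation CAT-MH as the analysis baseline even when surveys are repeated.
3. Give enrolled one meaning throughout. Say whether the 1,000 in the power statement counts students randomised or students attending, and report both numbers by arm.

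Items 2 and 3 are mainly wording. Item 1 is wording too if everyone randomised is already surveyed. Otherwise the five 8-weekly assessments cost at most 5 × $20 = $100 in incentives per non-attender, or $20 for week 8 alone. Because the CAT-MH includes suicidality, more surveys also mean some additional alert follow-up. The protocol gives no alert rate, so this is not priced here.
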